6.1.1. Instructions for storage and handling

The current retest period for storage at room temperature is 24 months. In addition, the drug substance is insensitive to the influence of light. The tablets are packaged in HDPE bottles, which contain 140 tablets. They should only be stored in the pack provided. The storage temperature should not exceed 25°C.

6.1.2. Concomitant medications

6.1.2.1. Permissible concomitant medication / therapies

Sorafenib inhibits a variety of liver metabolic enzymes in vitro. Although interaction studies showed no influence on the kinetics of substrates of CYP3A4 (such as midazolam), CYP2D6

(such as dextrometorphane) and CYP2C19 (such as omeprazole) making interactions with medications metabolized by these enzymes less likely, the clinical impact of the inhibition of CYP 2B6, CYP2C8/9 by sorafenib may result in increased levels of substrates of these enzymes. A complete list of potential medications can be found at

<http://medicine.iupui.edu/clinpharm/DDIs/table.aspx> (provided by the Indiana University School of Medicine). Sorafenib inhibits P-gp, which could increase levels of the following substrates of P-gp: *Amiodaron, Atorvastatin, Chinin, Chinidin, Ciclosporin, Clarithromycin, Dihydropyridin-Calciumantagonisten, Diltiazem, Erythromycin, Esomeprazol, Grapefruit, Itraconazol, Ketoconazol, Lansoprazol, Methadon, Nefazodon, Nelfinavir, Omeprazol, Pantoprazol, Piperin, Ritonavir, Saquinavir, Simvastatin, Spironolacton, Tacrolimus, Tamoxifen, Verapamil.*

Sorafenib also inhibits glucuronisation enzymes UGT 1A1 and 1A9, which could lead to increased levels of *Estradiol or Propofol*.

However, several of these medications are obligatory standard treatments after allo-SCT (exemplary listed in table 1). Since their use could interfere with the pharmacokinetics and -dynamics of sorafenib pro-active monitoring for plasma levels (cyclosporine, tacrolimus), liver toxicity or sorafenib side effects is warranted.

Patients requiring treatment with warfarin should proactively be monitored for their INR values.

Table 1. Standard concomitant medications post allo-SCT that may interfere with sorafenib metabolism and plasma levels

Indication	Liver Metabolism of sorafenib	
	unlikely	possible
Pneumocystis carinii prophylaxis	
 • pentamidine inhalation 	
 • trimethoprim-sulfamethoxazole
Antibacterial therapy	
 • penicillin • cephalosporin antibiotics • betalactam antibiotics • quinolone antibiotics: levofloxacin, ciprofloxacin 	
 • macrolide antibiotics
Antifungal therapy	
 • caspofungin • amphotericin B (conventional and liposomal preparation) 	
 • 'azole' antifungals (i.e., fluconazole, ketoconazole, itraconazole, voriconazole, posaconazol)
Immune-suppression		
 • cyclosporine, tacrolimus, mycomofetilphenolate, mTor-inhibitors, cortisone
Anti-viral	
 • acyclovir, valganciclovir 	

Anti-hypertension	
 • beta-Blocker • amlodipine • furosemid, torasemid • ACE-inhibitors 	
 • Diltiazem, verapamil
-------------------	--	--

(based on known interactions of the indicated drugs with liver metabolizing enzymes of sorafenib, Source: <http://medicine.iupui.edu/clinpharm/ddis/table.asp>)

6.1.2.2. *Non-permissible concomitant medication / therapies*

- Any other anticancer chemotherapy including cytotoxic, targeted, immunologic, investigational, or antiangiogenic agents other than sorafenib are not allowed.
- There is no clinical information on the effect of CYP3A4 inducers on the pharmacokinetics of sorafenib. Substances that are inducers of CYP3A4 activity (e.g. rifampin, St. John's wort, phenytoin, carbamazepine, phenobarbital, and dexamethasone) are expected to increase metabolism of sorafenib and thus decrease sorafenib concentrations. There are no clinical data evaluating the effect of chronically co-administered CYP3A4 inducers on sorafenib's efficacy. Since there is a possibility of decreased sorafenib efficacy upon chronic co-administration of CYP3A4 inducers with sorafenib, chronic co-administration of CYP3A4 inducers with sorafenib, should be avoided to the extent possible.
- Patients taking narrow therapeutic index medications should be monitored proactively. These medications include phenytoin, quinidine, carbamazepine, phenobarbital, cyclosporin and digoxin.
- St. John's wort containing remedies are not permitted.

6.1.2.3. *Donor lymphocyte infusion*

- **Donor lymphocyte infusions (DLI) are not part of this trial, and are generally not planned**, because there is no experience regarding the potential of Sorafenib to aggravate a graft versus host response in the context of DLI. Sorafenib may alter the activation and function of immunologically relevant cellular sub-fractions and thus the efficacy, tolerability and side effects (elicitation of GvHD) of DLI. DLI may, however, be performed at the discretion of the treating physician.

6.1.2.4. Growth factors

The use of myeloid and erythroid growth factors post allo-SCT is generally not planned and any indication should be carefully assessed and reasonable.

6.2. Sorafenib/placebo - dose modifications and delays

Sorafenib/placebo therapy will be taken according to defined dose levels:

Dose level 1 (starting dose) : 2 tablets / day (1-0-1)
 Dose level 2 (escalated dose): 3 tablets / day (1-0-2)
 Dose level 3 (targeted dose) : 4 tablets / day (2-0-2)

The starting dose will be dose level 1 in order to allow adaption to the drug and avoid acute toxicities. If after the run-in phase of 2 weeks dose level 1 was well tolerated (no probably related AE's > grade 1), the next dose level (dose level 2) will be commenced and maintained for the next 4 weeks. If, after this time, dose level 2 was well tolerated the targeted standard dose level (dose level 3) will be administered indefinitely. Dose level 3 is the targeted dose.

6.2.1. Dose delay and modifications for non-hematological toxicity

In case of severe toxicities, dose reductions or delays will be required as specified in Table 2. It illustrates dose modifications for all non-hematologic toxicities according to CTCAE Version 4.02 in the CRF, except for skin toxicities, which will be detailed separately below. These recommendations pertain, if the adverse event is considered related to sorafenib.

Table 2: Non-hematologic criteria for dose delay and dose modification of sorafenib (except skin toxicity)^a

Grade	Dose Delay	Dose modification
0-2	none	No change
3	Interrupt until \leq grade 2 ^b	Resume with one dose level below last dose level ^c
4	OFF protocol therapy	OFF protocol therapy

a. Excludes nausea/vomiting that has not been pre-medicated, and diarrhea.

b. If no recovery within an up to 28-day delay, treatment will be permanently terminated unless the patient is deriving clinical benefit

c. The dose of study drug may be increased from the reduced dose level stepwise every 4 weeks to dose level 3 if tolerated (no re-appearance of non-hematological toxicity \geq grade 0-2). In case toxicity recurs, and repeated dose reductions are required (more than 2), treatment will be indefinitely performed with dose level 1. When this is also not tolerated study treatment will be permanently discontinued.

For the purpose of dose modifications, patients experiencing Hand-Foot syndrome should have their signs and symptoms graded according to the following system (see below). Other skin toxicities will be graded according to CTCAE Version 4.02.

- Grading for Hand-Foot Syndrome

Grade 1

Numbness, dysesthesia/paresthesia, tingling, painless swelling or erythema of the hands and/or feet and/or discomfort, which does not disrupt normal activities.

Grade 2

Painful erythema and swelling of the hands and/or feet and/or discomfort affecting the patient's activities.

Grade 3

Moist desquamation, ulceration, blistering or severe pain of the hands and/or feet and/or severe discomfort, which cause the patient to be unable to work or perform activities of daily living.

According to the grade and incidence of skin toxicity (including rash and hand-foot syndrome) for a given patient, the following dose modification schedule will be followed (see Table 3).

Table 3: Skin Toxicity Criteria for Dose Modification of Sorafenib

Toxicity Grade	Dose modification	Dose level after interruption
Grade 1	Maintain dose level	Institute supportive measures
Grade 2 1 st appearance	Interrupt until resolved to grade 0-1	Resume with one dose level below the dose level prior to interruption ^a
2 nd or 3 rd appearance	Interrupt until resolved to grade 0-1	Resume with dose level 1 and maintain indefinitely
4th appearance	Decision whether to discontinue treatment permanently	
Grade 3 1 st appearance	Interrupt until resolved to grade 0-1	Resume with one dose level below the dose level prior to interruption ^a
2 nd appearance	Interrupt until resolved to grade 0-1	Resume with dose level 1 and maintain indefinitely
3 rd appearance	Decision whether to discontinue treatment permanently	

^a For patients who require a dose reduction for grade 2 or 3 rash or hand-foot syndrome, the dose of study drug may be increased subsequently to the targeted dose level after 4 weeks of therapy at the reduced dose without the appearance of rash or hand foot syndrome \geq grade 1.

Patients with discomfort due to hand foot syndrome may be treated with topical emollients, low potency topical steroids, or urea-containing cream; emollients and urea cream can be used early as a prophylactic measures to prevent extensive skin toxicity (see also

prophylactic measures [26] [27] [28]. All other grade 3 toxicities related to study drug result in a permanent dose reduction.

- Sorafenib-associated diarrhea

Diarrhea is a common side effect of sorafenib but is usually of low-to-moderate grade. It either resolves while treatment is continued, with appropriate anti-diarrhoic treatments, or once sorafenib is discontinued.

Appropriate prophylactic and/or therapeutic drugs that have been reported to be effective in the treatment of sorafenib-associated diarrhea are loperamide (4 mg after first loose stool, 2 mg after every other loose stool) or racecadotril (Tiorfan®) (one 100mg capsule three times daily). *However, an important differential diagnosis of Sorafenib associated diarrhoea in the context of allo-SCT is intestinal GvHD, which should be histologically confirmed or excluded via endoscopy of the sigmoid / colon.*

- Sorafenib-associated hypertension

The dose modification schedule for treatment emergent **hypertension** during sorafenib dosing should be followed (see table 4). Patients' blood pressure (BP) measurements will be monitored and appropriate treatment to effectively control hypertension under sorafenib-treatment is strongly recommended.

Blood pressure measurements considered out of normal range are diastolic ≥ 100 mmHg and systolic ≥ 160 mmHg, or a ≥ 20 mmHg increase in diastolic measurement if the measurement was previously within normal limits.

Table 4: Management of Treatment-Emergent Hypertension

Grade of Event (NCI-CTCAE V4.02)	Management/Next Dose
Grade 1 asymptomatic and transient	Consider increased BP monitoring
Grade 2 asymptomatic and diastolic BP <110 mmHg	Begin anti-hypertensive therapy and continue sorafenib/placebo
Grade 2 symptomatic/persistent OR Diastolic BP ≥ 110 mmHg OR Grade 3	Sorafenib/placebo should be stopped* until symptoms resolve and diastolic BP returns to ≤ 100 mmHg. Treat patient with anti-hypertensives and when sorafenib/placebo is restarted, reduce by 1 dose level.** (refer to section 7.3) If diastolic BP not controlled to ≤ 100 mmHg on therapy, reduce sorafenib/placebo by another dose level and monitor BP closely***
Grade 4 life-threatening	Discontinue protocol therapy

Please note that specific criteria are not completely identical to NCI-CTCAE V4.02 criteria.

* Patients requiring a delay of >28 days should discontinue the study treatment

** May be able to resume full dose later.

*** Patients requiring >2 dose reductions should discontinue the study treatment.

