5.8. Withdrawal of patients from study treatment

In accordance with the Declaration of Helsinki, each subject may voluntarily withdraw from the study at any time without giving reasons for this decision. The decision to withdraw from the study treatment must be without any prejudice for the patient.

Study treatment of a patient **may** also be terminated by the investigator for one of the following reasons:

- Severe (S)AE which make it necessary to stop study treatment
- Abnormal laboratory value(s) which make it necessary to stop study treatment
- Abnormal test procedure result(s) which make it necessary to stop study treatment
- Non-compliance with the study protocol
- Physicians decision

Study treatment **has to be** terminated for one of the following reasons:

- Subject withdrew consent
- Relapse of disease
- Pregnancy

If the investigator withdrew the patient prematurely, he has to inform the patient about his decision and has to record the primary reason for the withdrawal in the patient's medical record and on the end of treatment CRF. Safety assessments will be performed at the date of discontinuation and approximately one month after last dose of study drug. Final study evaluations will be done according to the evaluation plan outlined in table 6.

If the patient caused the premature withdrawal, all data before termination may be used for final analysis. After termination they will be followed until end of study or death. Safety assessments will be performed at the date of discontinuation and approximately one month after last dose of study drug. Off study evaluations will be done according to the evaluation plan outlined in table 6.

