6.2.2. Dose delay and modifications for hematological toxicity

There is little experience regarding Sorafenib-induced hematological toxicity after allo-SCT. However, there may be hematological toxicity in the context of a compromised bone marrow reserve, GvHD or subsequent to viral infections, requiring dose delay and modification according to table 5.

Table 5: Hematologic Criteria for Dose Delay and Dose Modification of Sorafenib/Placebo

Toxicity Grade	Dose Delay	Dose Modification
Grade 0-2	Treat on time	No Change
Grade 3	Treat on time	DECREASE one dose level ^b
Grade 4	DELAY ^a until ≤Grade 2	DECREASE one dose level ^b

a If no recovery after 28-day delay, treatment will be discontinued unless patient is deriving clinical benefit

b If more than 2 dose reductions are required, treatment will be discontinued

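### The 28-day toxicity stop is waived for a benefit that a blinded site cannot observe, and section 5.8 and the section 6 tables do not agree on which toxicity stops are mandatory

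*Protocol*

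**What the plan says.** Protocol section 6.2.1, Table 2 (non-hematological toxicity other than skin), interrupts drug at grade 3 until recovery to grade 2 or below. Footnote b adds: "If no recovery within an up to 28-day delay, treatment will be permanently terminated unless the patient is deriving clinical benefit". Section 6.2.2, Table 5 (hematological toxicity), has a parallel footnote to its grade 4 delay: "If no recovery after 28-day delay, treatment will be discontinued unless patient is deriving clinical benefit". Table 4 (hypertension) has no waiver: "Patients requiring a delay of >28 days should discontinue the study treatment".

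Grade 4 events are unconditional stops in Table 2 and, for hypertension, in Table 4. Section 5.8 has two lists. Reasons for which treatment *may* be terminated include "Severe (S)AE which make it necessary to stop study treatment". Reasons for which it *has to be* terminated are withdrawal of consent, relapse and pregnancy; no toxicity appears there.

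On more than two dose reductions, Table 2 footnote c says that if "repeated dose reductions are required (more than 2), treatment will be indefinitely performed with dose level 1", with a stop only if that level is not tolerated. Table 4 says "Patients requiring >2 dose reductions should discontinue the study treatment" and Table 5 says "If more than 2 dose reductions are required, treatment will be discontinued".

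**The concern.** A waiver based on clinical benefit makes sense where a site can see a response, such as a shrinking tumour. Here the patient starts in remission and the aim is to stay there. The protocol does not define the term, name an assessor or link it to a test, so the 28-day limit may have no force.

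The second problem is that a site looking up when it must stop for toxicity finds different answers in section 5.8 and in section 6. At stake are equal protection of patients across sites and a consistent record of exposure and discontinuation in a trial that lists the toxicity comparison as a secondary objective.

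**Working it through.** No figure in the plan depends on this point, so the check is mainly a comparison of passages.

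**Step 1: whom can the waiver reach?**
- CHR must be confirmed by marrow within 14 days before randomization (5.2).
- Relapse ends study drug at once (5.8, 6.7.2).
- Patients and investigators are blinded (5.6).

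Any patient whose drug is on hold at day 28, and not already stopped, is thus relapse-free as far as is known, in either arm.

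**Step 2: what could a site use to judge benefit?**
- Marrow is examined only at baseline and at relapse or suspected relapse (Table 6, footnote h).
- Flt3-ITD PCR from blood is scheduled in Table 6 at baseline and at month 30 or end of study. Section 7.1.3 adds month 24, when treatment ends.
- Blood counts are taken at every visit. They can reveal relapse but do not otherwise show an effect of study drug.
- The response criteria cited in 12.1 are not linked to either footnote.

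**Step 3: the two possible readings.**
- *Benefit means still in remission.* It is then true of every patient from step 1, and no patient is left for whom the limit binds.
- *Benefit means remission due to study drug.* The site would have to infer the arm. Remission says little about that. Under the plan's assumptions in 11.2 (2-year relapse-free survival 65% on placebo, 82.5% on sorafenib) and 1:1 allocation, a patient relapse-free at two years is on sorafenib with probability 0.825 / (0.825 + 0.65) = 0.825 / 1.475 = 0.56, against 0.50 before any follow-up. This ignores what the toxicity itself suggests about the arm. If a site used that, the judgement would rest on the side effect and not on benefit.

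**Step 4: the stopping passages side by side.**

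| Situation | Table 2 | Table 4 (hypertension) | Table 5 (hematological) | Section 5.8 |
|---|---|---|---|---|
| No recovery by 28 days | stop, with waiver | should stop, no waiver | stop, with waiver | toxicity under *may* only |
| Grade 4 | off therapy | discontinue | delay, then reduce | toxicity under *may* only |
| More than two reductions | continue at dose level 1 | should stop | will stop | not listed |

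Table 3 (skin) sets no time limit. Skin is expressly outside Table 2, so this is a separate rule and not a contradiction.

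Hypertension is the one overlap. The scope of Table 2 is given as "It illustrates dose modifications for all non-hematologic toxicities according to CTCAE Version 4.02 in the CRF, except for skin toxicities", with no exclusion of hypertension, while the hypertension paragraph of 6.2.1 sends the reader to Table 4. The direction is there, but the scope statement of Table 2 was not adjusted to match it.

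The text before Table 2 calls dose reductions or delays required and, shortly after, calls the contents recommendations. That adds to the doubt about which stops are mandatory.

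**Step 5: effect on the analyses.** The primary comparison follows intention to treat (11.1, 11.4), so neither the log-rank test nor its type I error changes. The per-protocol set excludes major protocol violations (11.1). Whether a hold beyond 28 days is a violation depends on how the waiver is read.

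**The case against.** Four stronger readings are tempting, and the document supports none of them.

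- *A site may give drug during unresolved toxicity.* The footnotes lift only permanent termination. The instruction to hold until grade 2 or below stays in both tables, so the waiver lengthens a hold. This removes the most serious harm one might infer.
- *The tables give conflicting outcomes for the same delay.* They cover different toxicities and may differ on purpose, including on more than two reductions. Only hypertension falls under two tables, and the text points to Table 4.
- *Section 5.8 lets a site continue after a grade 4 event.* Its optional item concerns events that make stopping necessary, and section 6 can supply that necessity. The mandatory list does not claim to be complete. What remains is that 5.8 omits the grade 4 stops, does not refer to section 6, and no passage says which governs.
- *The effect falls mainly on sorafenib.* This is plausible, since the Table 2 rules apply to events considered related to the drug, but the protocol gives nothing from which to size it.

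It can also be said that investigator discretion is normal in toxicity management. That is fair, but discretion needs something observable to act on, and the waiver supplies nothing.

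**Conclusion.** The point holds in this limited form. The 28-day limit in Tables 2 and 5 can be waived for every patient it reaches, or turns on a guess at the arm, so it sets no limit that a site must observe. Section 5.8 and the section 6 tables do not agree on the mandatory grade 4 stops. The tables also diverge on more than two reductions, possibly by design but without saying so.

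The conclusion rests on three facts stated in the protocol (CHR at entry, stop at relapse, blinding) and on the absence of any definition of clinical benefit in it. The number of patients is unknown, because no rate of delays beyond 28 days is given. The consequences are holds of open length, discontinuation that depends on site and page, and less consistent patient protection and exposure data. The primary test is untouched. The point is worth correcting, but it does not threaten the efficacy conclusion.

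**What to change.** Amend the wording in three places.

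1. Reconcile section 5.8 with the section 6 tables so that the mandatory stops agree, for instance by cross-reference, and state which passage governs.
2. Adjust the scope of Table 2 to the direction already given in 6.2.1 that Table 4 is followed for hypertension, and say whether the differing rules on more than two reductions are intended to be toxicity-specific.
3. Reconcile the waiver in Tables 2 and 5 with a blinded trial in remission, so that whatever condition the sponsor keeps can be observed and recorded by a blinded site.

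Which clinical rule applies in each case is for the sponsor to decide. The cost is amendment text, with no new data and no new patients. The downside is slightly less investigator discretion.

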9.1. Definition of Adverse Event (AE)

An Adverse Event (AE) is any untoward medical occurrence in the patient administered a pharmaceutical product that does not necessarily have a causal relationship with this treatment. An AE is therefore described as any unfavourable and unintended sign (including laboratory result), symptom, or disease temporally (timely) associated with the use of a medicinal (investigational) product, whether or not related to the product.

The reporting of abnormal laboratory values should be avoided unless they lead to clinical consequences that are not routine.

Events such as nausea, vomiting or constipation should not be regarded as AE (unless Grade III / IV and worsening of symptoms after treatment start) until day +100 after transplantation.

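### The dose-modification rules in 6.2.1 and 6.2.2 give opposite instructions on re-escalation after some grade 3 toxicities and do not say what a one-level reduction means at dose level 1

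*Protocol*

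**What the plan says.** Section 6.2 of the protocol defines three dose levels: 2, 3 and 4 tablets a day. It explains the lowest as the entry point: "The starting dose will be dose level 1 in order to allow adaption to the drug and avoid acute toxicities". Level 1 is scheduled for 2 weeks and level 2 for the next 4. Nothing below level 1 is defined.

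Section 6.2.1 then sets the reductions for non-hematological toxicity.

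- **Table 2** (non-hematologic, skin excepted). After a related grade 3 event, interrupt, then "Resume with one dose level below last dose level". Footnote c adds: "The dose of study drug may be increased from the reduced dose level stepwise every 4 weeks to dose level 3 if tolerated".
- **Table 3** (skin). The first grade 2 and the first grade 3 appearance each lead to one level down. Its footnote allows a later increase after rash or hand-foot syndrome.
- **Text after Table 3**, closing the advice on treating hand-foot syndrome: "All other grade 3 toxicities related to study drug result in a permanent dose reduction".
- **Table 4** (hypertension). One row covers symptomatic or persistent grade 2, diastolic pressure of 110 mmHg or more, and grade 3. Treatment stops and restarts one level lower, with the footnote "May be able to resume full dose later". If diastolic pressure stays uncontrolled, a further level is taken off.

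Section 6.2.2, **Table 5** (hematologic), calls for one level down at grade 3 and at grade 4. It does not mention re-escalation.

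**The concern.** These are instructions that an investigator must act on at once, in transplanted patients, at about 10 to 20 centres. The protocol itself says that experience with sorafenib toxicity after transplantation is limited (sections 3.4 and 6.2.2).

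Two things look wrong. First, the same grade 3 event seems to be governed by a sentence that makes the reduction permanent and by a footnote that lets the dose go back up. Second, a patient still on the starting level who meets a reduction trigger is sent to a level that the protocol does not define.

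If both hold, two centres could manage the same event differently and each cite the protocol. Exposure to study drug would then partly reflect which line a site had read.

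**Working it through.** The protocol states no figure on this point, so there is none to reproduce. The check has two parts: the grade 3 rules side by side, then each reduction rule applied to each defined level.

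**1. Can the dose go back up after a related grade 3 event?**

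| Event | Table rule | Sentence after Table 3, read literally |
|---|---|---|
| Non-hematologic, non-skin (Table 2) | Yes, stepwise to level 3 | No |
| Hypertension (Table 4) | Yes, full dose possible later | No |
| Rash or hand-foot syndrome (Table 3) | Yes | Probably outside the sentence |
| Hematologic (Table 5) | Not mentioned | No; no conflict |

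The conflict is therefore confined to Tables 2 and 4. Within Table 2 it does not reach diarrhea or nausea and vomiting without pre-medication, because footnote a takes these out of the table.

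Both footnotes are permissive. A site that never re-escalates breaches neither rule. A site that does re-escalate follows the footnote and breaches the sentence.

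**2. Does one level down lead to a defined level?**

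Defined levels are L = 1, 2, 3. The new level is L − 1, or L − 2 where Table 4 asks for a second step.

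| Trigger | From level 3 | From level 2 | From level 1 |
|---|---|---|---|
| Table 2, grade 3 | 2 | 1 | undefined |
| Table 3, first grade 2 | 2 | 1 | undefined |
| Table 3, first grade 3 | 2 | 1 | undefined |
| Table 4, stop-and-reduce row | 2 | 1 | undefined |
| Table 5, grade 3 | 2 | 1 | undefined |
| Table 5, grade 4 | 2 | 1 | undefined |
| Table 4, second step | 1 | undefined | undefined |

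All six one-level triggers fail at level 1 and all six work at levels 2 and 3. The second step in Table 4 also fails for a patient who was on level 2 when the hypertension arose.

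**3. Do the rules on more than two reductions close the gap?**

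Tables 4 and 5 end treatment when more than two reductions are required. Table 2 footnote c continues at level 1 in that case, and stops if level 1 is not tolerated either. Without re-escalation in between, the number of reductions that can be carried out from level L is L − 1:

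- From level 3: 2. The third one required is more than two, so these rules apply.
- From level 2: 1. The second one required already has no level to go to, and 2 is not more than 2.
- From level 1: 0. The first one required has no level to go to.

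The gap is thus open for a patient who is on level 1 with no earlier reduction or only one. The first case includes every patient in the 2-week run-in (14 days).

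**The case against.** **On the grade 3 sentence.** Its position supports a narrower meaning. It closes the skin paragraph, ahead of the items on diarrhea and hypertension. Table 3 covers skin toxicity including rash and hand-foot syndrome, while its footnote allows re-escalation for those two only. The sentence could therefore mean skin toxicities other than those two, and it would then not touch Table 2 or Table 4. This reading is reasonable and may be what was intended. It does not remove the problem, because the wording refers to toxicities related to study drug and does not limit itself to skin.

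**On level 1.** Not every rule fails there. The repeat-appearance rows of Table 3, and the grade 4 rows of Tables 2 and 4, can be applied. Footnote c shows that level 1 is thought of as a floor in Table 2. Section 5.8 lets the investigator end treatment for a severe adverse event or an abnormal laboratory value. All of this stands and narrows the point. But footnote c's sentence is written for the case after more than two reductions and does not extend to Tables 3, 4 or 5. Section 5.8 is a general discretion and does not say what a one-level reduction means at level 1.

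**Stronger readings that the protocol does not support.**

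- A reader might infer that escalation under 6.2 clashes with 9.1, which says: "Events such as nausea, vomiting or constipation should not be regarded as AE", up to day +100 unless grade III/IV and worsening after treatment start. Read together, the sections give one determinate rule: milder events of this kind before day +100 do not count against escalation. The overlap is also limited. With the earliest start on day +60, the decisions fall on day 60 + 14 = 74 and day 60 + 42 = 102, so the second is after day +100 for everyone. The first falls by day +100 only for starts up to day 100 − 14 = 86.
- A reader might infer that membership of the per-protocol set becomes undecidable. Section 11.1 leaves major deviations to a compilation by the coordinating investigator, and nothing makes a dose-modification choice a major violation.
- A reader might infer that sites will diverge. The text shows only that they can.

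**Conclusion.** The point holds in two parts.

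First, read as written, the sentence on permanent reduction contradicts the re-escalation footnotes of Tables 2 and 4. If it was meant for certain skin toxicities only, its scope is missing. Either way the text needs correcting. Table 5 is not in conflict.

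Second, six one-level triggers across Tables 2 to 5 have no defined result at level 1. This concerns all patients during the scheduled first 14 days, and later any patient on level 1 after fewer than two reductions. That last limit assumes that reductions are counted without re-escalation in between. How many patients would meet a trigger there cannot be derived from the protocol.

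The rules apply alike to both blinded arms. The analysis is by intention to treat, so the primary log-rank test and the sample size do not change. The effect is on patient safety and on consistent exposure across sites.

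**What to change.** Two wording changes, both for the clinical lead to decide:

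1. Reconcile the sentence after Table 3 with Table 2 footnote c and the Table 4 footnote so that one rule remains for each event, or state which toxicities the sentence covers.
2. In Tables 2 to 5, state what applies when a one-level reduction is triggered at level 1. In Table 4, also cover the second step for a patient who started from level 2.

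Which rule is right is a clinical matter and none is proposed here; the passages only have to agree.

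The same edit can clear two small faults in the lines concerned. Footnote c sets its re-escalation condition against a range of grades that begins at 0, which cannot be applied. Table 4 refers to a section 7.3, which the protocol does not contain.

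The cost is amendment text and a note to sites. No procedure, visit or analysis changes.
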